9.4.1.2.2. Sensitivity Analyses for the Primary Estimand for Part B

The following sensitivity analyses will be performed for the primary efficacy endpoint to explore the robustness of the primary efficacy analysis. Additional details will be provided in the SAP for Part B.

Control-Based Multiple Imputation

This sensitivity analysis will assess the robustness of the primary endpoint results due to possible violation of the MAR assumption. Missing TIS40 data will be handled in the same fashion as described in Section 9.4.1.2.1 except that missing TIS data for patients in the ravulizumab group who do not experience intercurrent events will be multiply imputed assuming a trajectory similar to the placebo group.

The same analysis method as described in Section 9.4.1.2.1 will be used.

Tipping Point Analysis:

In this analysis, TIS40 data will be handled in the same fashion as described in Section 9.4.1.2.1 except that missing data from participants in the ravulizumab group who do not experience the intercurrent events will be multiply imputed with an adjustment to the imputed values. The size of the adjustment can be varied and the adjustment which results in a non-significant p-value will be considered the "tipping point".

9.4.1.2.3. Supplemental Analysis of Primary Endpoint Using Treatment-Policy Estimand

Under the treatment-policy estimand, all available TIS40 data will be used for analysis regardless of whether patients experience intercurrent events. For example, suppose a participant becomes a TIS40 responder after initiation of acute therapy with standard DM treatment. In that case, the observed response will be used, unlike treating the participant as a non-responder described in the primary estimand. Other conventions described in Section 9.4.1.2.1 will remain the same.

9.4.1.2.4. Analyses of Key Secondary Efficacy Endpoint(s) for Part B

The comparison of the treatment groups for the mean IMACS-TIS at Week 50 of the Randomized Controlled Period will be based on the randomized set.

Consistent with the primary composite estimand strategy, for participants who experience the intercurrent events, TIS scores will be assumed to be zero (no improvement) from the point of intercurrent event occurrence. Missing data for other participants will be considered missing at random.

A mixed model for repeated measures will be used for the statistical analysis of the TIS data. The MMRM model will include the observed TIS values at post-baseline visits as the dependent variable. The model will include categorical effects of treatment, study visit, treatment-by-study visit interaction, and the randomization strata. An unstructured covariance matrix will be used to model the correlations among repeated measurements within each participant. The Kenward-Roger method will be used to estimate the denominator degrees of freedom. The least square means, the associated SEs, the p-value and 95% CIs of the mean IMACS-TIS at week 50 for each treatment and difference between ravulizumab and placebo will be calculated.

A control-based imputation and tipping point analysis will also be performed on the mean IMACS-TIS as sensitivity analysis.

A supplemental analysis will also be performed using the Treatment Policy Estimand strategy.

All other continuous key secondary endpoints will be analyzed similarly. Further details will be provided in the SAP for Part B.

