| 9.4.1.1.1. Analyses of Primary Efficacy Endpoint for Part A | Revised primary analysis to remove weighted Generalized Estimating Equations (wGEE) model and replace with Barnard's unconditional exact test for difference of proportions. | Revised method proposed to simplify the statistical inference and to enable use of single imputation for missing TIS data. |
| Section 9.4.1.1.2 Analyses of Secondary Efficacy Endpoint for Part A | Removed wGEE and logistic model for secondary endpoints in Part A. | To align analysis method for secondary binary endpoints with the primary endpoint |
| Section 9.4.1.2.1 Analyses of Primary Efficacy Estimand and/or Endpoint for Part B | Revised primary analysis from wGEE to a Cochran-Mantel Haenszel (CMH) test with Multiple Imputation (MI) for missing data not due to intercurrent events. | Revised method to simplify the statistical inference and to enable use of multiple imputation for missing TIS data. |
| Section 9.4.1.2.2 Sensitivity Analysis for the Primary Estimand for Part B | Removed reference of observation weighting | No longer applicable due to revised primary endpoint analysis, |
| | Edits to purpose of the sensitivity analyses. | For clarification of sensitivity analyses. |

| Section # and Name | Description of Change | Brief Rationale |
|---|--|--|
| Section 9.4.1.2.4 Analyses of Key Secondary Efficacy Endpoint(s) for Part B | Removed adjusted baseline covariates. | To align with revised approach in 9.4.1.2.1 |
| Section 9.4.1.2.5 Multiplicity Adjustment for Part B | Minor edits. | For clarification. |
| Section 9.5.1 Part A Interim Analyses | Added statement on potential additional analysis in Part A (at the time of the interim analysis which may be generated and reviewed by an unblinded team (independent of the study study). | For clarification . |
| Section 9.5.2 Part B Interim Analyses | Revised the Sample Size Reestimation (SSR) to align with the primary endpoint and changed the percentage of participants from 50% to 30%. Further clarification regarding SSR. | To align with revised primary endpoint and to include additional details of SSR for clarification. |
| Section 9.6 Data Monitoring Committee | Corrected DMC to IDMC in 2 instances as IDMC is used for study. | Correction. |
| Section 10.2.6 Dissemination of Study Data | Outlined that the results will be posted after the global end of the study. | For clarification. |

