|---|---------------|----|-----|-------|----------|-----------|--------|------|------|----|---|
| Study Visit | 1 | 2 | 3 | 4 | 5 | 6 | 7 | 8 | 9/ET | | Participants who discontinue/withdraw from the study should complete the study visit (if at the site |
| Study Day | D-42 to -1 | D1 | D15 | D71 | D127 | D183 | D239 | D295 | D351 | | for a scheduled visit) or return for an UV as soon as possible within a week and complete the ET Visit 8 weeks after the participant's last dose of study |
| Window (day) | | | ± 2 | ± 3 | ± 3 | ± 3 | ± 3 | ± 3 | ± 3 | | intervention. In addition, a follow-up phone call 21 weeks (± 1 week) after the participant's last dose of study intervention will be performed to collect |
| Weeks | Up to 6 weeks | | W2 | W10 | W18 | W26 | W34 | W42 | W50 | | information on concomitant medications, non- pharmacologic therapies and procedures, and AEs (see Section 7.2 for more details). |
| | | | | | | | | | | | Participants who will not enter the OLE Period will complete the assessments for Week 50 but not receive an infusion at Week 50 (see Section 6.1.1 for more details). |
| Informed consent | X | | | | | | | | | | |
| Assessment of inclusion/ exclusion criteria | X | | | | | | | | | | |
| Medical history | X | | | | | | | | | | |
| DM history | X | | | | | | | | | | |
| ACR/EULAR criteria | X | | | | | | | | | | |
| Weight | X | X | X | X | X | X | X | X | X | | |
| Height | X | | | | | | | | | | |
| HIV-(1 and 2) testing | X | | | | | | | | | | |
| Vital signs | X | X | X | X | X | X | X | X | X | X | On dosing days, vital signs will be taken before study intervention administration and after the participant has been resting for at least 5 minutes (see Section 8.2.4). |

Table 2: Schedule of Activities: Screening Through End of the Randomized Controlled Period for Part B (Phase 3)

| Period/Phase | Screening | | | Rando | mized Co | ontrolled | Period | | | UV | Notes |
|---------------------------------------|------------------|----|-----|-------|----------|-----------|--------|------|------|----|--|
| Study Visit | 1 | 2 | 3 | 4 | 5 | 6 | 7 | 8 | 9/ET | | Participants who discontinue/withdraw from the study should complete the study visit (if at the site for a scheduled visit) or return for an UV as soon as |
| Study Day | D-42 to -1 | D1 | D15 | D71 | D127 | D183 | D239 | D295 | D351 | | possible within a week and complete the ET Visit 8 weeks after the participant's last dose of study |

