Abbreviations: ACR/EULAR = American College of Rheumatology/European League Against Rheumatism; ADA = antidrug antibody; anti-MDA5 = antimelanoma differentiation-associated protein 5; anti-NXP2/MJ = antinuclear matrix protein 2; anti-TIF1= anti-transcription intermediary factor 1; C5 = complement component 5; CDA-IGA = Cutaneous Dermatomyositis Activity Physician's Global Assessment; CDASI = Cutaneous Dermatomyositis Disease Area and Severity Index; DM = dermatomyositis; DM-DSQ = dermatomyositis disease symptoms questionnaire; EQ-5D-5L = European Quality of Life Health 5-item questionnaire dimensions 5 level; FACIT = Functional Assessment of Chronic Illness Therapy; HAQ = health assessment questionnaire; IMACS-TIS = International Myositis Assessment and Clinical Studies-Total Improvement Score; IL6 = interleukin 6; MDAAT = Myositis Disease Activity Assessment Tool; MMT-8 = manual muscle testing subset of 8 muscles; PD = pharmacodynamic(s); PK = pharmacokinetic(s); PROMIS = Patient-Reported Outcomes Measurement Information System; RCP = Randomized Controlled Period; sC5b-9 = soluble terminal complement complex; SF-36 = Short Form Health Survey (36 questions version); TEAE = treatment-emergent adverse event; TESAE = treatment-emergent serious adverse event; TIS20 = ≥ 20-point improvement response on IMACS-TIS; TIS40 = ≥ 40-point improvement response on IMACS-TIS

 Table 8:
 Mapping Objectives to Endpoints/Estimands for Part B (Phase 3 Portion)

| Objectives | Endpoints/Estimands | |
|---|--|--|
| Primary | | |
| To determine the effect of ravulizumab compared with placebo in the treatment of DM based on improvement in Total Improvement Score (TIS) IMAC-TIS ^a | IMACS-TIS ^a (TIS40) response at Week 50 of the Randomized Controlled Period as per defined composite estimand (see Section 3.1) | |
| Key Secondary | | |
| To assess the efficacy of ravulizumab compared with placebo in the treatment of DM based on improvement in components of IMACS and other myositis activity measures | TIS at Week 50 Change from baseline in MMT-8 at Week 50 Change from baseline in extra-muscular disease activity based on MDAAT at Week 50 Change from baseline in CDASI Activity Score at Week 50 | |
| Secondary | | |

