## 4.3. Secondary Endpoints

All secondary endpoints will be analyzed using the Randomized Set. There will be no formal testing of the secondary endpoints. Nominal p-values will be presented for endpoints where statistical testing is performed. Handling of the relevant IEs (acute therapy with standard DM treatment/prohibited medications and treatment discontinuation due to AE, lack of efficacy, or death) is described within each of the endpoints.

#### 4.3.1. Total Improvement Score at Week 26

The Total Improvement Score (TIS) at Week 26 will be analyzed using an MMRM. Any data following the relevant IE will be set to missing, and the missing value will be imputed using the LOCF before the relevant IE.

The MMRM will include the observed TIS values at post-Baseline scheduled visits (Weeks 2, 10, 18, and 26) as the dependent variable. The model will include categorical effects of treatment, study visit, and treatment-by-study visit interaction. An unstructured covariance matrix will be used to model the correlations among repeated measurements within each participant. The Kenward-Roger method will be used to estimate the denominator degrees of freedom. If the model using the unstructured correlation matrix fails to converge, then an alternative correlation structure resulting in the best model fit based on the Quasi-likelihood information criterion (QIC) (ie, smallest QIC) will be used among the following correlation structures: autoregressive (1), Toeplitz, and exchangeable.

At each visit, the least square (LS) mean with corresponding standard error and 80% CIs will be displayed by treatment arm. The LS mean treatment difference (ravulizumab - placebo) in TIS at Week 26 will be presented along with the 80% CI along with the corresponding p-value.

Descriptive statistics will also be generated by treatment arm at each scheduled visit.

LS means (± SEM) figure of TIS by treatment arm will be plotted.

#### 4.3.2. Change From Baseline in Cutaneous Dermatomyositis Disease Area and Severity Index Activity Score at Week 26

The Cutaneous Dermatomyositis Disease Area and Severity Index (CDASI) instrument measures activity and damage in the skin while the Clinician or Clinical-Investigator examines the participant. A summary score of Total activity and total damage are collected at each scheduled visit. Any data following the relevant IE will be set to missing, and the missing value will be imputed using the LOCF before the relevant IE.

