Change from Baseline in in Total Activity Score at Week 26 will be analyzed using an MMRM. The MMRM model will include the observed Total Activity Score values at post-Baseline visits (Weeks 2, 10, 18, and 26) as the dependent variable. The model will include categorical effects of treatment, study visit, treatment-by-study visit interaction, and adjust for baseline Total Activity Score. An unstructured covariance matrix will be used to model the correlations among repeated measurements within each participant. The Kenward-Roger method will be used to estimate the denominator degrees of freedom. If the model using the unstructured correlation matrix fails to converge, then an alternative correlation structure resulting in the best model fit based on the QIC (ie, smallest QIC) will be used among the following correlation structures: autoregressive (1), Toeplitz, and exchangeable.

At each visit, the LS mean with corresponding standard error and 80% CIs will be displayed by treatment arm. The LS mean treatment difference (ravulizumab - placebo) in the change from Baseline in Total Activity Score at Week 26 will be presented along with the 80% CI and corresponding p-value.

Descriptive statistics of actual values and change from Baseline in Total Activity Score will also be generated by treatment arm at each scheduled visit.

LS mean ( $\pm$  SEM) figures of change from Baseline in Total Activity Score by treatment arm will be plotted.

Summaries of Total Damage Score will be descriptive. actual values and change from Baseline in total damage score will be presented by treatment arm and scheduled visit.

#### 4.3.3. Change From Baseline in 5 IMACS CSMs at Week 26

Change from Baseline in the 5 IMACS Core Set Measures (CSMs) at Week 26 will be analyzed using an MMRM. The 5 IMACS CSMs are comprised of (1) extramuscular disease activity, (2) physician global activity assessment, (3) patient global activity assessment, (4) manual muscle testing (MMT-8), and (5) HAQ. Any data following the relevant IE will be set to missing, and the missing value will be imputed using the LOCF before the relevant IE.

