For each of the 5 CSMs, the outcome variable is change from Baseline in CSM at Weeks 2, 10, 18, and 26 and will include fixed effects of treatment arm (ravulizumab, placebo), visits (Weeks 2, 10, 18, and 26), treatment by visit interaction term, and adjustment for baseline of the core set measure. An unstructured covariance matrix will be used to model the correlations among repeated measurements within each participant. The Kenward-Roger approximation will be used to calculate the denominator degrees of freedom. If the model using the unstructured correlation matrix fails to converge, then an alternative correlation structure resulting in best model fit based on the QIC criterion (ie, smallest QIC) will be used among the following correlation structures: autoregressive (1), Toeplitz, and exchangeable.

Within each CSM, the LS mean with corresponding standard error and 80% CIs will be displayed by treatment arm and visit. The LS mean treatment difference (ravulizumab - placebo) in the CSM at Week 26 will be presented along with the 80% CI along with the corresponding p-value.

In addition, change from Baseline in each of the muscle enzymes (sixth CSMs) will be analyzed using the MMRM model as specified above. A separate model for each muscle enzyme (creatine

kinase, aldolase, alanine aminotransferase, aspartate aminotransferase, and lactate dehydrogenase) will be generated.

Descriptive statistics of actual and change from Baseline in the 5 CSM will also be generated by treatment arm at each scheduled visit.

#### 4.3.4. Response Related to Muscle Enzymes - Normalization of Most Abnormal Baseline Enzyme at Week 26

Muscle enzymes are classified as the following 5 laboratory parameters: creatine kinase, aldolase, alanine aminotransferase, aspartate aminotransferase, and lactate dehydrogenase. For each participant, at Baseline, the most abnormal muscle enzyme is the laboratory parameter with the highest ratio (result/ULN) among the 5 laboratory parameters. Normalization of the most abnormal Baseline enzyme will be achieved if the result is less than the ULN (eg, ratio  $\leq 1$ ).

Participants will be defined as a responder at Week 26 if:

- 1. The participant achieves normalization of the most abnormal baseline muscle enzyme (eg, ratio  $\leq$  1) at Week 26 and
- 2. The participant did not have a relevant IE (defined in Section 4.2 and Table 2) up to and including Week 26 and
- 3. The participant did not have normal muscle enzymes at Baseline.

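### Part B's Holm-tested change-from-baseline models (MMT-8, MDAAT extra-muscular activity, CDASI activity) list no baseline value, although the Part A SAP adjusts the same measures; the Part B SAP should add it

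*Protocol*

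**What the plan says.** Protocol Section 9.4.1.2.4 describes a mixed model for repeated measures with observed TIS values as the dependent variable: "The model will include categorical effects of treatment, study visit, treatment-by-study visit interaction, and the randomization strata". It then states: "All other continuous key secondary endpoints will be analyzed similarly", and leaves further details to the Part B SAP, which is not among the documents.

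Table 8 in Protocol Section 3 lists four key secondary endpoints for Part B. One is TIS at Week 50. The others include "Change from baseline in MMT-8 at Week 50 Change from baseline in extra-muscular disease activity based on MDAAT at Week 50", and the fourth is change from baseline in CDASI activity score at Week 50. Section 9.4.1.2.5 tests the four by Holm's method if the primary endpoint succeeds.

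The Part A SAP treats the two kinds of endpoint differently:
- TIS (4.3.1), no baseline term: "The model will include categorical effects of treatment, study visit, and treatment-by-study visit interaction".
- CDASI activity (4.3.2), with baseline: "The model will include categorical effects of treatment, study visit, treatment-by-study visit interaction, and adjust for baseline Total Activity Score".
- Core set measures, including MMT-8 and extramuscular activity (4.3.3): "treatment by visit interaction term, and adjustment for baseline of the core set measure".

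The Part B schedule (Protocol Table 2) has seven post-baseline visits in the randomized period: "W2 | W10 | W18 | W26 | W34 | W42 | W50".

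**The concern.** The listed terms suit TIS, which is itself scored from baseline. They are not the natural terms for a raw change score, which depends on its own starting value through regression to the mean. Nothing in the protocol adds that starting value for the other three endpoints, so the confirmatory text is less specific than the Part A SAP on the same measures.

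At stake is the precision of three of the four Holm-tested endpoints, where the smallest p-value faces 0.05/4 = 0.0125, and how far a chance baseline difference carries into the estimated effect. The randomization stratum (CDASI activity at most 14 or above 14) adjusts CDASI coarsely and may catch the skin part of MDAAT, but it does not target MMT-8. The sample size was set for TIS40 alone.

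**Working it through.** **Plan's own figure.** Section 9.2.2 assumes 23% versus 58% (23% plus 35 points), two-sided 0.05, 90% power, 2:1 allocation and 20% dropout. The pooled two-proportion formula gives 30 placebo and 90 evaluable participants in all; 90/0.8 = 112.5, rounded up to 113, against 114 stated. The figure reproduces and does not depend on the baseline covariate. No size or power is stated for the key secondary endpoints.

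**Assumed inputs.** The documents give no baseline-to-Week-50 correlation r, no SD and no pattern of correlation over visits. I take r = 0.3, 0.5, 0.7, 0.8 and k = SD at Week 50 / SD at baseline, with baseline variance 1.

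**Step 1. Baseline with a slope for each visit.** Week 50 variance of the change is 1 + k² − 2rk without baseline and k²(1 − r²) with it. For k = 1 the ratio is 2(1 − r)/(1 − r²) = 2/(1 + r). SE inflation from omitting baseline:
- r = 0.3: √(2/1.3) − 1 = 24%
- r = 0.5: √(2/1.5) − 1 = 15%
- r = 0.7: √(2/1.7) − 1 = 8%
- r = 0.8: √(2/1.8) − 1 = 5%

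These apply to MMT-8, and to MDAAT as upper values.

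**Step 2. Unequal variances.** k = 1.3 gives 11, 5, 0.5 and 0.1%. k = 0.8 gives 41, 32, 26 and 25%.

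**Step 3. CDASI, whose stratum is already in the model.** If baseline is normal, a 50/50 split at the cut-off explains 0.637 of its variance and a 30/70 split 0.576. With r constant over visits, the inflation beyond the stratum is 9–11, 6–7, 3–4 and 2%. A simulation of the repeated-measures model (complete data, 61 versus 30, 3,000 replicates) gave 7.9, 5.0 and 2.7% at r = 0.3, 0.5 and 0.7, so these are on the high side. If r falls over visits the stratum helps less, because it too enters as one effect common to all visits: 16, 10, 5 and 2–3% under mixed decay (random intercept, exponential decay and 10% measurement error).

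**Step 4. Zero-setting.** Section 9.4.1.2.4 sets TIS to zero after intercurrent events. If changes are likewise set to zero for an assumed 20% of participants, independently of baseline, with k = 1 and mean change 0 or −0.8 SD, the inflation is 10–12% at r = 0.5 and 5–7% at r = 0.7.

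**Step 5. One common slope, as in Part A.** Under an unstructured covariance the fitted slope is a weighted average over the seven visits, so it may not suit Week 50. Inflation it removes, k = 1, r = 0.3, 0.5, 0.7, 0.8:
- constant r: 24, 15, 8, 5% (all of it)
- mixed decay: 14, 9, 6, 5%
- exponential decay with 10% measurement error: 12.6, 8.8, 6.1, 4.7%, which is 53 to 87% of the visit-specific gain
- exponential decay without error: 5, 2, 1, 0.5%

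**Step 6. Cost of visit-specific slopes.** One degree of freedom per visit; with 91 evaluable (0.8 × 114), √(1 + 1/(91 − 4)) − 1 = 0.6% of SE.

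**Step 7. Chance imbalance.** With 76 versus 38, one standard error of the baseline difference is √(1/76 + 1/38) = 0.20 SD. At k = 1, (1 − r) of it carries into the unadjusted change difference: 0.10 SD at r = 0.5, 0.06 SD at r = 0.7.

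**The case against.** The strongest reply is that this is a deferral that the sponsor has already shown how to fill. For Part A, Protocol Section 9.4.1.1.2 says only that a mixed repeated-measures model will be used. The Part A SAP then added baseline for the change endpoints, left it out for TIS, and recorded no change to the planned analyses (4.10). The Part B SAP may well do the same. That stands: the point concerns the protocol text as it reads, not a proven final omission. It does not remove the point, because the protocol lists terms and extends them to endpoints they do not suit.

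Timing is also partly covered. Section 9.4 requires the SAP before database lock, and the possible unblinded interim uses TIS data and goes to the IDMC (9.5.2). Still, that interim may come at about 30% of participants, well before lock, and covariates for confirmatory endpoints are best fixed before it.

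A reader might infer that copying the Part A form would not help because a common slope recovers little at Week 50. That is so only under exponential decay with no measurement error, where r = 0.3 at Week 50 implies about 0.95 at Week 2; clinician-rated scales are not error-free. A reader might also turn the SE figures into power gains, but the documents state no power for these endpoints, and a simple conversion ignores the zero-setting. Nor does the summary of changes show that these terms were deliberately removed: it describes superseded text and does not say which covariates it means.

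**Conclusion.** The point holds as a specification gap with a cheap remedy. As written, three Holm-tested change-from-baseline endpoints have no baseline value in the model, while the sponsor's Part A SAP adjusts the same measures. Type I error, the estimand and the primary analysis are unaffected, so a reader should not infer that the planned test is invalid.

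The size rests entirely on assumed correlations and SDs. With equal variances, about 5 to 24% of the Week 50 SE is at issue for MMT-8, and at most that for MDAAT; for CDASI it is about 2 to 11% if the correlation is constant over visits. The zero-setting in Step 4 shrinks the gain. It almost vanishes at correlations of 0.7 or more if the Week 50 SD is 1.3 times the baseline SD. In the visit-specific scenarios examined, the downside is at most about the 0.6% degree-of-freedom cost.

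**What to change.** In the Part B SAP, before any unblinded look at Part B, state that the repeated-measures model for change in MMT-8, MDAAT extra-muscular activity and CDASI activity also includes the continuous baseline value of that endpoint, alongside the CDASI randomization stratum. Exempt TIS explicitly. Carry the same sentence into Protocol Section 9.4.1.2.4 at the next amendment; no separate amendment is needed.

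Preferably add the baseline-by-visit interaction as well, because Part B has seven post-baseline visits over 50 weeks and a common slope gives the full gain only if the correlation with baseline is constant. This part is a refinement; the baseline value itself is the main request.

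The cost is one sentence and, with the interaction, one model degree of freedom per visit. The baselines are already collected (Protocol Table 2), and no new data or design change is needed.
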